5.2 Neostigmine

5.2.1 Dosage Forms and Strengths: 0.5 mg/mL, 5 mg of Neostigmine in 10 mL vials and 1 mg/mL, 10mg of Neostigmine in 10 mL vials.

5.2.2 Recommended Dose and Administration: 70 mcg/Kg up to a total of 5 mg, intravenously slowly over a period of at least 1 minute.

6. Study Procedures

6.1. Intraoperative Anesthesia Care

All patients will receive a balanced general anesthesia with endotracheal intubation and volatile anesthetic agents. In order to avoid excessive sedation in the PACU, no long acting anesthetic agents (ketamine, dexmedetomidine, etc.) or narcotics (hydromorphone, morphine) will be allowed. Short acting narcotics (fentanyl) are allowed.

Patients will be randomized to receive either the Deep Neuromuscular Blockade (DNMB group) with Sugammadex reversal or Moderate Neuromuscular Blockade (MNMB group) with neostigmine reversal. The patients will be started on a continuous Rocuronium intravenous infusion following intubation. Insert recommendations and Institutional Standards will be used for Rocuronium. For the DNMB group, the rate will be adjusted and boluses given to maintain 1-2 post tetanic responses during the pneumoperitoneum. NMB will be reversed with Sugammadex at the end of surgery. For the MNMB group, the Rocuronium infusion rate will be adjusted to maintain 1-2 TOF responses and will be reversed with neostigmine at the end of surgery. The level of NMB will be assessed by the anesthetist with a standard nerve stimulator at 20 minute intervals for both groups.

During the surgical time-out and at the time of insufflation, the surgeon will be instructed to maintain the lowest insufflation pressure necessary for good surgical exposure and safety throughout the operation. All adjustments to the insufflation pressure will be directed by surgeon.

A clinical coordinator will calibrate the acceleromyography (TOF-Watch® SX, Organon Ireland Ltd., a subsidiary of Merck & Co., Inc., Swords, Co. Dublin, Ireland; pending availability due to product discontinuation by manufacturer) at the adductor pollicis muscle during induction prior to neuromuscular blockade, will record insufflation pressure changes during surgery and acquire the TOF ratio (TOFR) with the TOF-Watch® SX upon arrival of each patient to the PACU. Data will be collected from the electronic medical record (Anesthetic Record, PACU notes, Progress notes, Discharge summary, etc.) as well as a PACU survey.

6.2. Assessment of Outcomes

6.2.1. Depth of Neuromuscular Blockade: When possible, acceleromyography (TOF-Watch® SX, Organon Ireland Ltd., a subsidiary of Merck & Co., Inc., Swords, Co. Dublin, Ireland) at the adductor pollicis brevis muscle will be calibrated during induction but prior to muscle relaxation. The responses from the peripheral nerve stimulator and the site of application used by the anesthetist will be recorded at 20 minute intervals throughout the procedure. A TOF ratio per acceleromyography will be measured upon arrival to the PACU.

6.2.2. Insufflation pressure: Intra-abdominal insufflation time and pressure will be directed by the surgeon and recorded continuously by the clinical coordinator until the time of desufflation.

6.2.3. Surgical Exposure: At the end of the procedure, the surgeon will use the Surgical Rating Scale to describe the quality of surgical exposure. (Martini, Boon, Bevers, Aarts, & Dahan, 2013)

Table 1

The surgical rating score

- 1 *Extremely poor conditions:* the surgeon is unable to work because of coughing or because of the inability to obtain a visible laparoscopic field because of inadequate muscle relaxation. Additional neuromuscular blocking agents must be given
- 2 *Poor conditions:* there is a visible laparoscopic field, but the surgeon is severely hampered by inadequate muscle relaxation with continuous muscle contractions, movements, or

both with the hazard of tissue damage. Additional neuromuscular blocking agents must be given

3 *Acceptable conditions:* there is a wide visible laparoscopic field but muscle contractions, movements, or both occur regularly causing some interference with the surgeon's work. There is the need for additional neuromuscular blocking agents to prevent deterioration

4 *Good conditions:* there is a wide laparoscopic working field with sporadic muscle contractions, movements, or both. There is no immediate need for additional neuromuscular blocking agents unless there is the fear of deterioration

5 *Optimal conditions:* there is a wide visible laparoscopic working field without any movement or contractions. There is no need for additional neuromuscular blocking agents

6.2.4. Postoperative Pain: A Survey will be completed by the PACU nurse. The patient will be asked if INCISIONAL, VISCERAL and/or SHOULDER PAIN are present. The nurse will record Visual Analog Scale (VAS) pain score (1-10) for pain in general and for Shoulder Pain if present, recording these separately. All these will be recorded at 15, 45 and 90 minutes (if patient not previously discharged). Opioids administered by the PACU nurse will be measured in morphine equivalents.

6.2.5. Readiness to Discharge from PACU: Readiness to discharge from the PACU as determined by a modified version of the DASAIM discharge criteria scoring system (Gartner, Callesen, Kroman, & Kehlet, 2010) (Phillips, Street, Kent, Haesler, & Cadeddu, 2013) to be completed at 15, 45 and 90 minutes (if patient not previously discharged) after admission to the PACU. A patient will be considered ready for discharge if cumulative score is 4 or less and no single category has a score greater than 1.

DASAIM Discharge Criteria Scoring System (Gartner, Callesen, Kroman, & Kehlet, 2010)		
Sedation	0	Patient is fully awake
(Nurse Evaluation)	1	Patient is asleep, aroused by verbal stimulation
	2	Patient is asleep, aroused by physical stimulation
	3	Patient is asleep, cannot be aroused
Respiratory Rate	0	Respiratory rate > 10
(Nurse count)	1	Snoring, 10 < RR <30
	2	RR < 10 or RR > 30/min
	3	Periods of apnea or obstructive patterns
Oxygen Saturation	0	SpO2 ≥ 94%
(No supplemental oxygen for 10 minutes)	1	90% ≤ SpO2 < 94%
	2	85% ≤ SpO2 < 90%
	3	SpO2 < 85%

Systolic Blood Pressure	0	SBP \geq 100mmHg
	1	90mmHg \leq SBP < 100mmHg
	2	80mmHg \leq SBP < 90mmHg or SBP > 220mmHg
	3	SBP < 80mmHg
Heart Rate	0	50 < HR \leq 100
	1	100 < HR \leq 120
	2	40 < HR \leq 50 or 120 < HR \leq 130
	3	HR < 40 or HR > 130
Pain at rest	0	No pain
(Patient evaluation)	1	Light pain
	2	Moderate pain
	3	Severe pain
Nausea	0	No nausea or vomiting
	1	Light nausea or vomiting without previous nausea
	2	Moderate nausea and/or vomiting
	3	Severe nausea and/or vomiting

6.2.6. Postoperative Morbidity: Cystatin C will be drawn during pre-procedure and sent to external laboratory for analysis and calculation of the Cystatin C/Creatinine Ratio, to determine if the patient shows laboratory evidence of Sarcopenia. Postoperative lactate level will be drawn in the PACU as well as an arterial blood gas when an arterial line catheter is present. Overall postoperative morbidity will be recorded on POD 1, 3, 5 and 7 using the Postoperative Morbidity Survey assessed by chart review.

Morbidity type	Criteria
Pulmonary	De novo requirement for supplemental oxygen or other respiratory support (e.g., mechanical ventilation or CPAP)
Infectious	Currently on antibiotics or temperature $>38^{\circ}\text{C}$ in the last 24 h
Renal	Presence of oliguria ($<500\text{ mL/d}$), increased serum creatinine ($>30\%$ from preoperatively), or urinary catheter in place for a nonsurgical reason
Gastrointestinal	Unable to tolerate an enteral diet (either by mouth or via a feeding tube) for any reason, including nausea, vomiting, and abdominal distention
Cardiovascular	Diagnostic tests or therapy within the last 24 h for any of the following: de novo myocardial infarction or ischemia, hypotension (requiring pharmacological therapy or fluid therapy $>200\text{ mL/h}$), atrial or ventricular arrhythmias, or cardiogenic pulmonary edema
Neurological	Presence of a de novo focal deficit, coma, or confusion/delirium
Wound complication	Wound dehiscence requiring surgical exploration or drainage of pus from the operation wound with or without isolation of organisms
Hematological	Requirement for any of the following within the last 24 h: packed erythrocytes, platelets, fresh-frozen plasma, or cryoprecipitate
Pain	Surgical wound pain significant enough to require parenteral opioids or regional analgesia

CPAP = continuous positive airway pressure.

(Bennett-Guerrero, et al., 1999)

6.2.7. 30-Day Mortality and Readmission Rate: Patients will be contacted via phone 30 days after being discharged from the Hospital to collect mortality and readmission data. If research staff is not able to contact the patient, this data will be obtained from available medical records.

7. Adverse Events

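### The DASAIM table in section 6.2.5 gives some respiratory rates and systolic pressures two scores and leaves others with none, so PACU readiness is not uniquely defined

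*Combined protocol and SAP*

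**What the plan says.** Readiness to leave the PACU is secondary outcome 4.2.4, assessed at 15, 45 and 90 minutes. Section 6.2.5 calls the patient "ready for discharge if cumulative score is 4 or less and no single category has a score greater than 1". The table that follows has seven categories, each scored 0 to 3. The rows that matter here are:

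- **Respiratory rate.** Score 0 is "Respiratory rate > 10", score 1 is "Snoring, 10 < RR <30", score 2 is "RR < 10 or RR > 30/min" and score 3 is "Periods of apnea or obstructive patterns".
- **Systolic pressure.** Score 0 is 100 mmHg or more, with no ceiling. Score 2 covers 80 to below 90 mmHg and adds "or SBP > 220mmHg".
- **Heart rate.** Score 2 covers rates above 40 up to 50, and above 120 up to 130. Score 3 is "HR < 40 or HR > 130".

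Section 4.9 says that the DASAIM scores will be summarised by treatment. Nothing in the document says which row to use when a value fits two, or what to do when it fits none.

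**The concern.** A scoring table that feeds a yes/no rule has to place each value in exactly one row. Here two categories have a score 0 row with no upper limit, while the score 2 row of the same category claims the extreme upper values. Scores 0 and 2 lie on opposite sides of the limit of 1 per category, so the overlap affects the readiness flag itself and not just the total. Some boundary values are in no row at all.

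What is at stake is whether outcome 4.2.4 is measured in the same way for every patient. The respiratory item deserves care because the trial compares reversal strategies, and the Background links residual blockade to upper airway obstruction.

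**Working it through.** There is no stated figure to reproduce; the check is of the scoring logic. Each numeric category was coded as printed, and every whole-number value was tested for no row, more than one row, and rows on both sides of the limit of 1.

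| Value | Rows met | Effect on readiness |
|---|---|---|
| Respiratory rate above 30 | 0 and 2 | Opposite answers |
| Systolic pressure above 220 mmHg | 0 and 2 | Opposite answers |
| Snoring, rate 11 to 29 | 0 and 1 | Changes only if the other categories total exactly 4 |
| Respiratory rate 10, no apnea or obstruction | none | Undetermined |
| Heart rate 40 | none | Not ready under either neighbouring row |
| Oxygen saturation, any value | exactly one | None |

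**Overlap of 0 and 2.** Take a patient with a respiratory rate of 31 and all six other categories at 0.
- Using row 0: total = 0, highest category = 0, so ready.
- Using row 2: total = 2, which is within 4, but the highest category is 2, which exceeds 1, so not ready.

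The same holds for a systolic pressure of 221 mmHg. More generally, the answer flips whenever the other six categories would pass on their own (total of 4 or less, none above 1).

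**Overlap of 0 and 1.** Neither score breaks the single-category limit, so only the total can change the answer. Suppose sedation, oxygen saturation, pain and nausea each score 1 and the remaining two categories score 0.
- Snoring scored 0: total = 4 + 0 = 4, so ready.
- Snoring scored 1: total = 4 + 1 = 5, so not ready.

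If the others total 3 or less, with none above 1, the patient is ready either way.

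**Gap at respiratory rate 10.** Scores 0 and 1 need a rate above 10, and score 2 needs a rate below 10 or above 30. The value sits between a row that allows readiness and one that rules it out, so the table does not settle the result.

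**Gap at heart rate 40.** Score 2 needs a rate above 40 and score 3 a rate below 40. Both neighbouring scores exceed 1, so the patient is not ready either way. Only the total is uncertain, by 3 − 2 = 1 point.

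**The case against.** The strongest reply is that the scale is ordinal and its intent is plain. Score 2 names the high respiratory rate and the high systolic pressure explicitly, and reading those values as 0 would leave those clauses with no function. A nurse who takes the worst matching row gets one answer for every overlap. That is a sensible reading, but it is not written down, and it does nothing for a respiratory rate of 10, which matches no row.

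A second reply is that an equality sign may have been lost in typesetting or conversion. That could explain the two gaps, although such signs survive elsewhere in the same table. It cannot explain the overlaps, which come from score 0 rows without an upper limit.

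Third, PACU staff are blinded to group (section 4.7), so inconsistent row choice has no evident reason to favour an arm. This stands, and it limits the harm to noise.

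Some stronger readings are tempting but unsupported:

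- **Safety.** A reader might infer that a patient with an extreme respiratory rate or pressure could be sent out of the PACU on a score of 0. The rule appears under assessment of outcomes, and the documents do not say that it governs actual discharge.
- **Disagreement between nurses.** A reader might assume that different nurses score the three time points. The documents refer to nurse assessment but do not say that the nurse changes.
- **Two equal gaps.** A heart rate of 40 should not be counted alongside a respiratory rate of 10, because it leaves readiness unchanged.

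**Conclusion.** The table is wrong as written, and the defect reaches the threshold that defines secondary outcome 4.2.4. Two of the seven categories (respiratory rate and systolic pressure) give contradictory readiness results over part of their range. One value, a respiratory rate of 10, leaves readiness undetermined. The snoring overlap and the heart-rate gap are lesser faults.

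The practical size is probably small. The documents give no frequencies; the assumption here is that respiratory rates above 30 and pressures above 220 mmHg are uncommon in the PACU, while a rate of 10 or snoring at an ordinary rate is plausible. The primary endpoint and the sample size are untouched.

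A reader might size the effect at 1/48, about 2.1 percentage points of an arm's readiness rate per affected patient. The documents do not support that as a general figure. Section 4.9 names a summary of the DASAIM scores, not a comparison of readiness proportions. The 45- and 90-minute assessments are made only in patients not yet discharged, so later denominators may be below 48.

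**What to change.** Reconcile the respiratory, systolic pressure and heart rate rows so that every possible value falls in exactly one score, and state how snoring, apnea and obstruction combine with the measured rate. Which score applies to each value is for the investigators to decide. Use the reconciled table on the PACU data form.

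Optionally, record the raw respiratory rate, systolic pressure and heart rate at each assessment, so that the score and the readiness flag can be derived by one rule for all patients.

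The cost is one corrected table and a matching form. No extra assessment is needed, and the sample size does not change.

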7.1. General

All adverse events (AE) and serious adverse events (SAE) from study drug administration until hospital discharge. An AE is defined as an undesirable clinical outcome regardless of whether it was directly caused by the study drug. An AE applies to any unintended event with an onset during the study or an exacerbation in the severity of a preexisting condition. All reported AEs will be recorded in the database with their respective description, date, actions taken, outcomes and assessment of the relationship with the study drug and protocol. AEs will be categorized using the Common Terminology Criteria for Adverse Events (CTACE) version 4.0. For the events not characterized by CTACE, the following definitions for severity will be applied:

Mild: Awareness of signs or symptoms, but easily tolerated; are of minor irritant type; causing no loss of time from normal activities; symptoms would not require medication or a medical evaluation; signs or symptoms are transient.

Moderate Interferes with the patient's usual activity and/or requires symptomatic treatment.

Severe: Symptom(s) causing severe discomfort and significant impact of the patient's usual activity and requires treatment.

A Serious Adverse Event (SAE) is defined as an event which leads to:

- Death due to any cause
- Life-threatening condition
- Results in persistent or significant disability/incapacity
- Requires in-patient hospitalization or prolonged hospitalization
- Necessitates an intervention to prevent a permanent impairment of a body function or permanent damage to a body structure
- Results in congenital abnormality

All SAE's will be reported.

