4.6. Randomization

Once it has been determined that the patient meets all eligibility criteria, they will be randomized on a 1:1 ratio for Deep Neuromuscular Blockade and Sugammadex or Moderate Neuromuscular Blockade and neostigmine administration. Randomization will be done the morning of surgery by using REDCap randomization tool.

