4.9. Analysis Plans

Patients' demographic information, laboratory test results and concomitant medications, including neoadjuvant chemotherapy at baseline will be analyzed, with data summarized in tables listing the distributions of the variables along with the number of subjects per treatment arm in order to assess comparability. Patients' information on post-operative shoulder pain, nausea, vomiting, intubation and measures from Postoperative Morbidity Survey will be collected. The Fisher's exact test or Chi-square test will be applied to assess the association between two categorical variables. We will summarize the distribution of average and cumulative intraoperative insufflation pressure, Post Anesthesia discharge DASAIM scores, length of ICU and hospital stay by each treatment. We will use the student t-test or the Wilcoxon rank sum test to compare continuous variables between two different patient groups. Logistic regression will be utilized to assess the effects of patient prognostic factors, comorbidities and treatment on postoperative shoulder pain and postoperative morbidity.

Adverse event (AE) data will be summarized by frequency tables. The association between the types and severity of AE and the treatment will be evaluated.

5. Study Drug Information

Since both Sugammadex and Neostigmine are FDA approved, Insert recommendations and Institutional Standards will be followed for all study agents.

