8.6. Coverage of Expenses

The treated patients will not be reimbursed or compensated for participating in the Study.

Patient or insurance provider is responsible for all costs of surgery, including anesthesia and hospitalization. This includes all drugs involved in the study including Rocuronium, which is used as a neuromuscular blocking agent.

The study/treatment drugs Sugammadex and Neostigmine will be covered by the Sponsor and not billed to the patient. Other drugs utilized in this study will be used as per standard routine care. The site institution's research pharmacy department will maintain study supplies and record documentation. Additionally, they will also be responsible for the destruction of the supplies at the end of the study as per ICH/GCP guidelines, local regulations, and institutional policies. Supply should be shipped in marked vials to allow for non-blinded administration by the anesthesiologist.

Note: At conclusion of the study or upon drug expiration, the Merck GRS will be responsible for issuing a Drug Disposition Letter to the investigator for US based studies.

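### The adverse event window in 7.1 opens at reversal and closes at discharge, so as written it omits events confined to the randomised block, and it conflicts with other wording in section 7

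*Combined protocol and SAP*

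**What the plan says.** Section 7.1 gives the window for both adverse events (AEs) and serious adverse events (SAEs): "All adverse events (AE) and serious adverse events (SAE) from study drug administration until hospital discharge". The sentence has no verb, so it does not say whether events in that period are collected, recorded or reported.

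Section 5 (Study Drug Information) describes only sugammadex and neostigmine. Section 8.6 agrees: "The study/treatment drugs Sugammadex and Neostigmine will be covered by the Sponsor and not billed to the patient". Rocuronium appears there among the costs that fall to the patient or insurer: "This includes all drugs involved in the study including Rocuronium, which is used as a neuromuscular blocking agent".

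On timing, 6.1 says: "The patients will be started on a continuous Rocuronium intravenous infusion following intubation". For the deep-block arm it then says: "NMB will be reversed with Sugammadex at the end of surgery". Neostigmine is given at the same point in the moderate-block arm.

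The randomised comparison in 4.6 is "Deep Neuromuscular Blockade and Sugammadex or Moderate Neuromuscular Blockade and neostigmine administration", so block depth and reversal agent are allocated together.

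Section 6.2.7 adds a later contact: "Patients will be contacted via phone 30 days after being discharged from the Hospital to collect mortality and readmission data". Section 4.9 promises a comparison: "The association between the types and severity of AE and the treatment will be evaluated".

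**The concern.** The arms differ from the start of the infusion, first in block depth and, by the trial's hypothesis, in insufflation pressure. A safety window that opens only at reversal starts after that exposure has ended. A hypersensitivity reaction to rocuronium, a bleed, a circulatory disturbance under pneumoperitoneum or an operative injury could begin and be dealt with before the window opens.

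The protocol itself treats these as plausible. It excludes patients with known rocuronium hypersensitivity (4.5.2), lists cardiac and respiratory effects of insufflation and cites a blood-loss difference between block depths (section 1), and its surgical rating scale mentions a risk of tissue damage (6.2.3).

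What is at stake is the by-arm AE evaluation in 4.9. If deep block with lower pressure changes the frequency of intraoperative harm in either direction, a table built on the stated window would not show it.

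**Working it through.** No figure in the plan bears on this point, and the sample size calculation does not enter it. The check is to place the window on the trial's timeline and then test each sentence that might widen it.

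**Timeline**

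| Step | Source | Inside the 7.1 window? |
|---|---|---|
| Randomisation, morning of surgery | 4.6 | No |
| Rocuronium infusion, from after intubation | 6.1 | No |
| Pneumoperitoneum at the allocated block depth | 6.1, 6.2.2 | No |
| Reversal agent, end of surgery | 5, 6.1, 8.6 | Window opens |
| PACU and ward | 6.2.4 to 6.2.6 | Yes |
| Hospital discharge | 7.1 | Window closes |
| Phone contact 30 days after discharge | 6.2.7 | No |

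The opening point depends on what study drug means. Sections 5 and 8.6 both point to the reversal agents, and no section calls rocuronium a study drug. A randomised patient who never reaches reversal never enters the window.

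**Sentences that might widen the window**

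1. 7.1 goes on to define an AE by onset during the study. That phrase is wider than the window set at the head of the same section, and nothing says which governs. It does not clearly reach the 30-day contact either, because the synopsis ends participation at postoperative day 7 or discharge.
2. 7.1 also says that all SAEs are reported, and 7.6 says this holds whatever the attribution. Neither gives a start or end time, whereas the window sentence names SAEs expressly.
3. 7.3 provides a category for events caused by the procedure or by other anesthetic or surgical technique. The stated window leaves out almost all of the procedure.
4. 7.6 works in the other direction. It restricts non-serious AEs to grades 3 and 4 with at least possible attribution to a device, although the randomised intervention is a drug strategy. A non-serious intraoperative event could fail this filter even if the window were moved.
5. 7.5 follows unresolved SAEs to resolution, so the discharge limit applies to new events only.

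**Harm captured elsewhere**

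- The Postoperative Morbidity Survey (6.2.6) is completed on postoperative days 1, 3, 5 and 7. On day 1 it can see continued ventilation and, through its 24-hour items, possibly a transfusion or a treated arrhythmia from the operation. It has no item for an intraoperative hypersensitivity reaction that resolved, an operative injury or a bleed without transfusion.
- ICU and hospital stay, 30-day mortality and readmission are secondary outcomes (4.2.6).
- Insufflation pressure and the surgical rating score are recorded during or at the end of surgery, but they do not measure harm.

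The uncovered remainder is therefore mainly the event that starts and ends before reversal. After discharge, a death or readmission is known by arm and meets the SAE definition in 7.1 (death, in-patient hospitalization), but it falls outside the SAE window.

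**The case against.** The strongest reply is that section 7 taken whole does not say that intraoperative events are ignored. The window sentence is incomplete; the AE definition, the SAE sentences and the procedure-related category are all broader; and 7.6 defers to institutional practice and sponsor guidelines, which may set their own period and are not in the documents. Intraoperative SAEs may well be reported in practice. The morbidity objective also rests chiefly on the survey and the 30-day outcomes, not on the AE table. All of this stands, and it limits the point to a conflict in the text with a mainly intraoperative gap.

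Three stronger readings are tempting, and the documents do not support them.

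- A reader might infer that the AE comparison concerns the reversal agents alone. It does not: 7.1 counts an AE whatever its cause, so a harm of the block or pneumoperitoneum that appears after reversal is inside the window.
- A reader might infer that the gravest intraoperative event would leave no safety record. The SAE sentences in 7.1 and 7.6 could still bring it in.
- A reader might infer that harm after discharge is lost. Deaths and readmissions are collected and available by arm.

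Section 7.6 also gives a reason for limited collection: sugammadex is approved and its risks are documented. That supports lighter recording for the reversal agent. It does not extend to sustained deep block at lowered pressure, which is the other half of what is randomised.

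**Conclusion.** The point holds in this form. The window stated in 7.1 excludes events that begin and resolve during the randomised block, and new SAEs after discharge, while other sentences in section 7 point to a wider period. Followed literally, the window keeps intraoperative harm out of the AE evaluation in 4.9; followed loosely, what is recorded depends on which sentence staff apply. Either way the sections must be reconciled.

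In extent, the gap covers the whole randomised block period up to reversal in all 100 planned patients. The number of events missed cannot be estimated, because the documents give no intraoperative event rates. The discharge end is the lesser part: for deaths and readmissions the loss is one of SAE classification.

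The conclusion assumes that study drug means the two reversal agents, as sections 5 and 8.6 indicate, and that the institutional and sponsor reporting rules mentioned in 7.6 do not already fix an earlier start. The change should be made; the primary endpoint is not affected.

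**What to change.** 1. Reword 7.1, with a verb, so that AE and SAE collection starts at randomisation or at the start of the randomised block in every randomised patient, whether or not a reversal agent is given.
2. Reconcile 7.1, 7.3 and 7.6 so that they state one window. In 7.6, replace attribution to a device with attribution to the randomised strategy, meaning block and reversal together. Without this, moving the start date would still leave many intraoperative events unrecorded.
3. Classify deaths and readmissions learned at the 30-day contact as SAEs.
4. In 4.9, tabulate events by arm separately for before and after reversal.

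The cost is a wording amendment, somewhat more AE abstraction, and more expected intraoperative events to record. The sources are already in the plan: the anesthetic record and a coordinator recording pressures during surgery (6.1), and the 30-day call (6.2.7). Clinical care does not change.
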